5.9 Supportive care, Prohibited and Concomitant Medications/ Therapies

Participants must be instructed not to take any additional medications (including over-the-counter products) during the trial without prior consultation with the investigator.

5.9.1 *Prohibited medications/ therapies*

The following medications/ therapies are **prohibited** from Day 1 of protocol therapy until end of protocol therapy (last day of study agent or decision to end study agent(s) whichever occurs later):

- Co-medication that may interfere with study results; e.g. immuno-suppressive agents other than corticosteroids used for treatment of an IrAE are prohibited during the treatment period, unless discussed with the Study PI and felt to be of low clinical risk to the participant.
- Live attenuated vaccines
- Herbal and natural remedies

The following medications/therapies are prohibited any time after ASCT, active protocol treatment, or follow-up. If the patient receives one of these therapies in the absence of disease progression, the patient will be censored at the time of initiation.

- Other investigational therapy
- Concurrent anti-cancer therapy: chemotherapy, biological response modifiers, hormone therapy, surgery, palliative radiation therapy, or immunotherapy).

5.9.2 *Supportive care and permitted medications/ therapies*

With the exception of prohibited therapies (see [Section 5.9.1](#)), participants should receive prophylactic or supportive care as clinically indicated per institutional policies and suspected immune-related AEs (irAE) guidelines stated below.

Blood products

- *Platelet and/or red blood cell supportive growth factors or transfusions*
 - Permitted when applicable
- *Colony stimulating factors (CSFs)*
 - Permitted for treatment of neutropenia per institutional practice.

Corticosteroids

- *Topical, ocular, intra-articular, intranasal, and inhalational corticosteroids (with minimal systemic absorption)*
 - Permitted
- *Systemic corticosteroids*
 - Physiologic replacement doses permitted even if > 10 mg/day prednisone or equivalent.
- *Brief course of corticosteroids (< 3 weeks)*
 - Permitted for prophylaxis (e.g. contrast dye allergy)
 - Permitted for treatment of non-autoimmune conditions (e.g. delayed-type hypersensitivity reaction caused by contact allergen)

Strong CYP3A4/5 inhibitors

Closely monitor for AEs when administered concomitantly with brentuximab vedotin.

Required prophylaxis

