- d. Day 1 of Cycle 1 is defined as the day of first administration of brentuximab vedotin. Screening evaluations performed within 14 days prior to start of protocol therapy may serve as Day 1 baseline evaluations, **except** for pregnancy test which must be performed within 24 hours prior to Day 1 of protocol therapy.
- e. Activities (**except** imaging and response assessment) and safety assessment review to be performed within 72 hours prior to initiation of the new cycle.
- f. The 30 days post-last dose assessments to occur 30 (-2/+7) days post-last dose or, if > 30 days elapsed since last dose, within 7 days after decision to end treatment. Expedited reporting will occur during this period (see [Section 7.8](#)).
- g. The 100 days post-last dose assessments to occur 100 (-7/+28) days post-last dose or at initiation of a new anticancer therapy. Expedited reporting will occur during this period (see [Section 7.8](#)). Safety follow-up may be extended until resolution/ stabilization of reportable AEs.
- h. For participants who ended protocol therapy and have yet to progress/relapse, Active follow-up visit to occur at 3 months (± 14 days), 6 months (± 14 days), 12 months (± 28 days) and 18 months (± 28 days) from start of treatment until progression or initiation of new anticancer therapy.
- i. The Safety assessments/activities may be joint with Active Follow-up assessments/activities if the windows for the two visits overlap.
- j. The 3 month Active Follow-up activities to occur if the participant ended protocol therapy prior to the Cycle 4 Day 15 scan.
- k. The 6 month Active Follow-up activities to occur if the participant ended protocol therapy prior to Cycle 8.
- l. Long-term follow-up for those for all participants who have progressed/relapsed OR completed Active Response Follow-Up. Assessment to occur biannually or as requested by the Study PI via medical record review, review of social security registry/ public records, and/or telephone call.
- m. Informed consent process to be fully documented (see [Section 16.4](#)). Informed consent must occur prior to any research only (non-SOC) screening procedures.
- n. Eligibility criteria are detailed in [Section 3.0](#).
- o. Registration in a COH clinical trial management system (CTMS).
- p. Medical history to include a review of treatment history, any ongoing medical conditions and medical history pertaining to eligibility on study and involvement during study.

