11.1.2 Clinical Endpoints

Evaluable patients are defined as eligible participants who received at least one dose of the protocol treatment. Eligible participants who did not receive any protocol treatment will be considered in-evaluable, replaced, and excluded from all analyses.

Endpoint	Patients	Definition
Progression-Free Survival (PFS)*	Evaluable patients	Defined as the time from the first dose of study treatment to the first observation of disease relapse/progression or death from any cause, whichever occurs first. For patients who are alive and have not had disease relapse/progression at the last follow-up, it is censored at the time of last follow-up. If a patient receives non-protocol anti-HL treatment prior to disease relapse/progression, the patient will be censored at the time of non-protocol anti-HL treatment.

Endpoint	Patients	Definition
Overall Survival (OS)	Evaluable patients	Defined as the time from the first dose of study treatment to death from any cause. For patients alive at the last follow-up, it is censored at the time of last follow-up.
Cumulative Incidence of Non-Relapse Mortality (NRM)*	Evaluable patients	Defined as the time from the first dose of study treatment to non-disease related death. Disease relapse or progression is considered a competing risk. For surviving patients without disease relapse/progression at the last follow-up, it is censored at the time of last follow-up. If a patient receives non-protocol anti-HL treatment prior to disease relapse/progression, the patient will be censored at the time of non-protocol anti-HL treatment.
Cumulative Incidence of Relapse/Progression*	Evaluable patients	Defined as the time from the first dose of study treatment to disease relapse/progression. Death without relapse/progression is considered a competing risk. For surviving patients without relapse/progression at the last follow-up, it is censored at the time of last follow-up. If a patient receives non-protocol anti-HL treatment prior to disease relapse/progression, the patient will be censored at the time of non-protocol anti-HL treatment.
Overall response rate (ORR)	Evaluable patients with measurable disease post-ASCT	Proportion of patients achieving CR or PR [53]

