12.3 Statistical Analysis Plan

12.3.1 Power Estimation

The primary endpoint is 18-month PFS, as defined in [Section 11.0](#). Eligible participants who received at least one dose of the protocol treatment will be evaluable for the primary endpoint; eligible participants who did not receive any protocol treatment will be considered in-evaluable and excluded from all analyses.

Based on the AETHERA trial, the 18-month PFS rate in patients with relapsed/refractory HL who undergo ASCT followed by BV consolidation is approximately 65% (from the independent assessment data) [32]. We hypothesize that adding nivolumab to BV consolidation after ASCT will improve the 18-month PFS rate to 80%. A sample size of 59 evaluable patients will provide approximately 81% power for detecting the

increase in 18-month PFS from the baseline of 65% to 80% in this study at 1-sided type I error of 0.05. The power estimation is based on the exact binomial test. Operationally, the study treatment will be considered promising if at least 45 of the 59 evaluable participants are alive and progression-free at 18 months after the first dose of study treatment. The probability of observing at least 45 surviving and progression-free participants out of a total 59 participants, assuming different PFS rates, is shown in [Table 12.3.1](#).

Table 12.3.1 The probability of declaring the trial a success assuming different PFS rates

	True 18-month PFS rate			
	65%	70%	75%	80%
The probability of observing at least 45 participants (out of 59 total) being alive and progression-free at 18-month	0.044	0.18	0.48	0.81

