12.3.2 Analysis Plans

Patient demographics and baseline disease characteristics, including age, gender, medical history, and prior therapy, will be summarized using descriptive statistics. For continuous variables, descriptive statistics such as number, mean, standard deviation, standard error, median (range) etc. will be provided. For categorical variables, patient counts and percentages will be provided.

For all analyses, only eligible participants who received at least one dose of protocol treatment will be considered evaluable and included in the analyses. Eligible participants who did not receive any protocol treatment will be considered in-evaluable and excluded from all analyses.

PFS will be estimated using the product-limit method of Kaplan and Meier along with the Greenwood estimator of standard error. When there is no censoring in PFS prior to 18 months after the first dose of study treatment, the observed 18-month PFS will be compared to the baseline of 65% by one-sided exact test of binomial proportion. In case of censoring in PFS prior to 18 months after the first dose of study treatment (which are expected to be rare), the Kaplan-Meier estimate for 18-month PFS along with the Greenwood standard error estimator will be used for the testing of null hypothesis at 65%.

OS will be estimated using the product-limit method of Kaplan and Meier along with the Greenwood estimator of standard error. Cumulative incidence of relapse/progression and cumulative incidence of non-relapse mortality, as well as their confidence intervals will be estimated using competing risk methodology, treating the other event as a competing risk. Overall response rate will be estimated by the proportion of patients achieving either CR or PR among participants with measurable disease after ASCT, along with the exact binomial confidence interval.

Observed toxicities will be summarized by type (organ affected or laboratory determination such as absolute neutrophil count), severity (by NCI CTCAE v4.0 and nadir or maximum values for lab measures), date of onset, duration, reversibility, and attribution.

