16.5 Participant Withdrawal

Participants may withdraw from the study at any time and for any reason without prejudice. The withdrawal must be documented per institutional policies.

Participant withdrawal may consist of any of the following with regard to study procedures and data collection:

- Withdrawal from study treatment, but agreement to continue with active study procedures and chart review and follow-up procedures.
- Withdrawal from study treatment and all active procedures, but agreement for chart review and follow-up procedures.
- Withdrawal from study treatment, all active procedures, and any future data collection.

Participants who agreed to the collection of research blood samples may withdraw consent to use their specimens, if they are not yet processed as detailed in the consent form. Once the PI and site PI is notified of this withdrawal of informed consent, the research specimens will not be used in any research. At that time, any of the existing specimens will be destroyed.

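### Section 12.3.2 names no scale for the Kaplan-Meier test of 65%; read plainly, it passes an estimate of 44/59 that the exact test fails

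*Combined protocol and SAP*

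**What the plan says.** Section 12.3.1 designs the trial to detect an "increase in 18-month PFS from the baseline of 65% to 80% in this study at 1-sided type I error of 0.05", bases power on the exact binomial test, and gives the decision rule as a count: "the study treatment will be considered promising if at least 45 of the 59 evaluable participants are alive and progression-free at 18 months". The synopsis repeats this.

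Section 12.3.2 then gives two primary tests. With complete 18-month data it is a one-sided exact binomial test against 65%. Once any patient is censored earlier than that, which the section does not expect to happen often, a different test applies: "the Kaplan-Meier estimate for 18-month PFS along with the Greenwood standard error estimator will be used for the testing of null hypothesis at 65" percent. It gives no scale, test statistic or critical value for this second test, and no other section supplies them. The one-sided 0.05 level can reasonably be carried over from 12.3.1; the scale cannot.

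The documents give no expected censoring rate, but they do describe routes to censoring before 18 months:

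- **Non-protocol treatment.** Section 11.1.2: "the patient will be censored at the time of non-protocol anti-HL treatment". Section 5.9.1 on prohibited therapies says the same: "If the patient receives one of these therapies in the absence of disease progression, the patient will be censored at the time of initiation".
- **Full withdrawal.** Section 16.5 allows "Withdrawal from study treatment, all active procedures, and any future data collection".
- **An early last visit.** The Study Calendar (Section 10.0, footnote h) sets the final active follow-up visit at "18 months (± 28 days) from start of treatment until progression or initiation of new anticancer therapy".

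**The concern.** One patient censored before 18 months is enough to replace the exact test with the Kaplan-Meier test. Greenwood's variance can be used on several scales, and with 59 patients they do not agree near the decision boundary. The most natural reading, the untransformed one, sets a lower bar than the 45 of 59 on which the stated error and power rest. A borderline primary result would then depend on a choice not fixed before the data were seen.

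There is a second, smaller ambiguity. The 45-of-59 count in Section 12.3.1 is not limited to complete data. With 14 events and one censored patient, 59 - 14 - 1 = 44 patients are known to be event-free, so the literal count says not promising, while the Kaplan-Meier test passes.

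**Working it through.** **Inputs.** From Section 12.3.1: n = 59, null 65%, alternative 80%, one-sided 0.05 (critical value 1.645), bar 45 of 59. From Section 12.3.2: the two tests. Censoring patterns are assumptions, since the documents give no rate.

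**1. The plan's own figures.** P(X ≥ 45 | 59, p) at p = 0.65, 0.70, 0.75 and 0.80 is 0.0436, 0.1825, 0.4801 and 0.8124. Table 12.3.1 gives 0.044, 0.18, 0.48 and 0.81, so it reproduces. One patient fewer gives P(X ≥ 44 | 59, 0.65) = 0.0775, so 44/59 fails the exact test.

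**2. The Kaplan-Meier test at the boundary.** If all events precede the censoring, the estimate is S = k/59 and Greenwood's SE is √[S(1 - S)/59].

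- Untransformed: z = (S - 0.65)/SE. At 44/59: S = 0.7458, SE = 0.0567, z = 0.0958/0.0567 = 1.689; lower limit 0.7458 - 1.645 × 0.0567 = 0.6525.
- Log(-log): z = [log(-log 0.65) - log(-log S)] / [SE/(S·|log S|)]. At 44/59: (-0.842 + 1.227)/0.259 = 1.483; lower limit exp{-exp(-1.227 + 1.645 × 0.259)} = 0.638.

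| KM estimate | Exact p | Untransformed z (lower limit) | Log(-log) z (lower limit) |
|---|---|---|---|
| 44/59 | 0.0775, fails | 1.689 (0.6525), passes | 1.483 (0.6381), fails |
| 45/59 | 0.0436, passes | 2.035 (0.6716), passes | 1.731 (0.6564), passes |

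Other scales also split at 44/59: log gives z = 1.808 (passes), logit 1.529 and arcsine 1.606 (both fail).

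**3. Can the case occur?** Take one censored patient and vary how many events come before the censoring.

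- 15 events: untransformed z runs from 1.589 to 1.689. It is 1.640 after 9 events and 1.647 after 10, so it passes once at least 10 events precede the censoring. Log(-log) z is 1.406-1.483 and always fails.
- 14 events: untransformed 1.933-2.035, log(-log) 1.657-1.731. Both always pass.

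The disagreement is therefore a narrow band, reached when censoring is light and comes late relative to the events.

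**4. Error of the two-branch procedure.** Simulation with n = 59 and exponential PFS at 65% at 18 months; exact test if nobody is actually censored, otherwise untransformed Kaplan-Meier against 1.645. There were 400,000 runs per scenario, or 1,000,000 for the random-share, months 0-6 and three-patient last-28-days cases. Censoring times are uniform over the stated months.

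| Assumed censoring times | Overall one-sided error, untransformed |
|---|---|
| Random 0.5%, 1%, 2%, 5% of patients, months 0-18 | 0.048, 0.051, 0.054, 0.060 |
| One patient, months 0-6 | 0.051 |
| 1-6 patients, months 0-18 | 0.057-0.067 |
| 1-6 patients, months 12-18 | 0.059-0.072 |
| One or three patients, last 28 days | 0.070, 0.078 |

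Log(-log) in the same scenarios gives 0.037-0.051. With Weibull PFS (shape 0.7 or 1.5; 1-2% random, or 1, 3 or 6 patients over months 0-18 or 12-18) the ranges are 0.049-0.072 untransformed and 0.037-0.049 log(-log).

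The overall figures at low rates are diluted by trials with no actual censoring: only 21%, 38% and 62% of trials have any at 0.5%, 1% and 2%. Given that some occurs, the untransformed error at those rates is 0.063-0.066. With 0.5-2% random censoring, the two scales give opposite primary calls in 0.3-1.0% of trials when true PFS is 65% and in 0.7-2.5% when it is 80%.

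**5. The literal count.** If 45 known event-free patients are required even with censoring, and one or three patients are given censoring times over months 0-18, error is 0.028 or 0.009 and power at 80% is 0.74 or 0.55.

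**The case against.** The strongest reply is that an estimate paired with its own standard error is ordinarily an untransformed Wald test, so the scale is implied and the complaint is a preference between large-sample methods. That reading is fair, but it does not rescue the plan: it is the reading that lowers the bar to 44/59.

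A second reply is that the effect is narrow. An uncensored 44/59 goes to the exact test, the plan expects early censoring to be rare, and at 0.5-1% random censoring the overall error is 0.048-0.051. This stands and limits the weight of the point.

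Third, the highest figures (0.070-0.078) need censoring in the last 28 days. Section 5.7 continues disease-status follow-up to 5 years, which closes that route except for late-accrued patients if the data are cut when the last patient reaches 18 months, the follow-up planned in Section 12.1. This also stands; without those scenarios the maximum is 0.072, itself from assumed late censoring.

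Fourth, Section 12.3.2 is the specific rule for censored data and would probably be read as overriding the count in 12.3.1. That is likely, but the text does not say so.

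Finally, logit and arcsine would also keep the 45/59 bar when censoring is negligible. True; log(-log) is one sound choice, not the only one. What matters is naming the scale in advance.

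**Conclusion.** The point holds and is minor. The primary test under censoring has no stated scale, and its plain reading is looser than the 45-of-59 bar behind the stated level and power. The boundary results are exact arithmetic. The error figures, from about nominal to about 0.078, rest wholly on assumed censoring and PFS shapes; if censoring is as rare as the plan expects, the inflation is slight. What is affected is a borderline promising call in a single-arm phase 2 trial.

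**What to change.** In Section 12.3.2, state:

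*With any censoring before 18 months, success requires the one-sided 95% lower confidence limit for 18-month Kaplan-Meier PFS, using Greenwood's variance on the log(-log) scale, to exceed 65%.*

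In Section 12.3.1 and the synopsis, state:

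*The 45-of-59 count is the decision rule when no patient is censored before 18 months.*

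With no censoring the log(-log) test reproduces the 45/59 bar, so the two branches agree.

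The costs are modest:

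- Power at 80% is about 0.77-0.83, against about 0.82-0.88 for the untransformed test, most of whose extra power comes with inflated error.
- Log(-log) is still marginally above 5% (about 0.052-0.053) when exactly one patient is actually censored, and it gains nothing when that censoring is early (0.051 overall on both scales with one patient in months 0-6).
- The second sentence sets aside the more conservative literal count whenever anyone is censored.

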This is a single-arm, open-label Phase 2 study of nivolumab plus BV consolidation for patients with relapsed/refractory HL who have undergone ASCT. Participant screening can initiate 21 days post-ASCT. Participants must initiate protocol therapy within 30 to 60 days post-ASCT. Study PI can grant exception for a patient to start as late as 75 days post-ASCT with a reasonable justification for delay (e.g. recovery from post-ASCT toxicity) and this will not be a protocol deviation, nor require an exception to be filed. Nivolumab and brentuximab vedotin will be administered in 21-day cycles. BV and nivolumab will be administered on Day 1 of each cycle. Participants will receive up to 8 cycles of protocol therapy, or until unacceptable toxicity or disease progression. Response assessments will occur during screening, Cycle 4 Day 15, 30 days post-last dose, and at 12 and 18 months from start of treatment visits. The primary endpoint is 18-month progression-free survival. Secondary endpoints include overall survival, cumulative incidence of relapse/progression, cumulative incidence of non-relapse mortality, overall response rate, and toxicity.

Objectives:

Primary Objective

- Assess the efficacy of nivolumab plus brentuximab vedotin consolidation after autologous stem cell transplantation (ASCT) in participants with relapsed/refractory classical Hodgkin Lymphoma (HL), as assessed by 18-month progression-free survival (PFS).

Secondary Objective

- Estimate the overall survival (OS), the cumulative incidence of relapse/progression, the cumulative incidence of non-relapse mortality (TRM) in participants with relapsed/ refractory HL who receive nivolumab plus brentuximab vedotin consolidation after ASCT.
- Estimate the overall response rate to nivolumab plus brentuximab vedotin therapy in participants with measurable disease after ASCT.
- Establish the safety and tolerability of nivolumab plus brentuximab vedotin when used as consolidation after ASCT in participants with relapsed/ refractory HL.

Exploratory Objective

- Evaluate the Lymphoma Response to Immunomodulatory therapy Criteria (LYRIC) definition of indeterminate response to guide the management of patients regarding treatment past progressive disease.
- Explore the impact of nivolumab plus brentuximab vedotin therapy on immune reconstitution after ASCT.

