If the monitoring rule is met, the study PMT will review and assess the safety of the trial and submit a report outlining the findings and proposed action plans if any to the COH DSMC. The COH DSMC will review and make the decision to continue, modify, or permanently suspend accrual to the trial. At the end of the study with 59 evaluable participants, the 95% exact binomial confidence interval for the rate of such unacceptable AE will have a width of no more than 27%.

Eligibility Criteria

Inclusion Criteria

- Age: \geq 18 years
- ECOG performance status \leq 2
- Histologically confirmed diagnosis of classical Hodgkin lymphoma (excluding nodular lymphocyte predominant Hodgkin lymphoma) according to the WHO classification, with hematopathology review at the participating institution.
- Have high-risk relapsed or refractory Hodgkin lymphoma (HL), defined as at least one of the following:

- Primary refractory disease to front-line therapy.
- Relapse within 1 year of completing front-line therapy.
- Extranodal involvement at the time of pre-ASCT relapse.
- B symptoms at pre-ASCT relapse.
- More than one type of pre-ASCT salvage therapy required.
- Planning to receive or have received autologous stem cell transplantation (ASCT) per institutional standards as part of standard of care.
 - Pre-ASCT participants may consent but will not be eligible to begin treatment until after ASCT, and will have to fulfill all inclusion and exclusion criteria before starting protocol therapy.
 - All participants must initiate Day 1 of protocol therapy within 30-60 days post stem cell reinfusion. Study PI can grant exception for a patient to start as late as 75 days post stem cell reinfusion with a reasonable justification for delay (e.g. recovery from post-ASCT toxicity) and this will not be a protocol deviation, nor require an exception to be filed.
- Recovery from ASCT toxicity as defined as outpatient status , able to drink, eat normally, and do not need intravenous hydration prior to Day 1 of therapy
- Achieved at least stable disease to salvage treatment determined by PET/CT using 2014 Lugano classification prior to ASCT.
- Brentuximab vedotin naïve OR had at least stable disease by Lugano classification to prior brentuximab vedotin treatment
- ANC \geq 1000/mm³
- Platelets \geq 50,000/mm³
- Hemoglobin \geq 8 g/dL
- Total bilirubin \leq 1.5 x ULN OR 3 x ULN for Gilbert's disease
- AST and ALT \leq 2.5 x ULN

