Organ Function Criteria and Pregnancy11. ANC \geq 1000/mm³12. Platelets \geq 50,000/mm³13. Hemoglobin \geq 8 g/dL14. Total bilirubin \leq 1.5 x ULN OR 3 x ULN for Gilbert's disease15. AST and ALT \leq 2.5 x ULN16. Creatinine clearance* \geq 40 mL/min per 24 hour urine collection or the Cockcroft-Gault formula

* Calculated per institutional standard

$$\text{CrCl} \text{ (mL/min)} = \frac{(140\text{-age}) \times \text{actual body weight (kg)}}{72 \times \text{serum creatinine (mg/dL)}} \text{ (x 0.85 for females)}$$

Or

$$\text{CrCl} \text{ (mL/min)} = \frac{(140\text{-age}) \times \text{actual body weight (kg)}}{0.8136 \times \text{serum creatinine (umol/L)}} \text{ (x 0.85 for females)}$$

17. Forced expiratory volume in one second (FEV1) and carbon monoxide diffusion capacity (DLCO) (adjusted for Hb) \geq 50% adjusted18. WOCBP only: Negative urine or serum pregnancy test (minimum sensitivity 25 IU/L or equivalent units of HCG)

- If the urine test is positive or cannot be confirmed as negative, a serum pregnancy test will be required

ANC:	Date:
Plts:	Date:
Hgb:	Date:
ULN:	Date:
Bil:	
ULN: ALT:	Date:
ULN: AST:	Date:
ULN:	Date:
Serum Cr:	
Cr Cl:	

FEV1:	Date:
DLCO:	
Urine test:	Date:
Serum test:	

Contraception

19. Woman of childbearing potential (WOCBP): use two effective methods of contraception (hormonal or barrier method) or be surgically sterile, or abstain from heterosexual activity for the course of the study through 7 months post last dose of nivolumab.

- WOCBP defined as not being surgically sterilized or have not been free from menses for > 1 year.

Male: use two effective methods of contraception (barrier method) or abstain from heterosexual activity with the first dose of study therapy through 7 months post last dose of nivolumab.

Participant MRN (COH Only):

Participant Initials (F, M, L):

Institution:

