Very common	Increased AST, increased ALT, increased alkaline phosphatase, increased lipase, increased amylase, hypocalcemia, increased creatinine, hyperglycemia ^c , hypercalcemia, hyperkalemia, hypokalemia, hypomagnesemia, hyponatremia

System Organ Class	Adverse Reactions
Common	Increased total bilirubin, hypoglycemia, hypermagnesemia, hypernatremia, weight decreased

a Fatal cases have been reported in completed or ongoing clinical studies

b Frequencies of laboratory terms reflect the proportion of patients who experienced a worsening from baseline in laboratory measurements.

c Life-threatening cases have been reported in completed or ongoing clinical studies.

d Rash is a composite term which includes maculopapular rash, rash erythematous, rash pruritic, rash follicular, rash macular, rash morbilliform, rash papular, rash pustular, rash papulosquamous, rash vesicular, rash generalised, exfoliative rash, dermatitis, dermatitis acneiform, dermatitis allergic, dermatitis atopic, dermatitis bullous, dermatitis exfoliative, dermatitis psoriasiform, drug eruption and pemphigoid.

e Reported also in studies outside the pooled dataset.

f Musculoskeletal pain is a composite term which includes back pain, bone pain, musculoskeletal chest pain, musculoskeletal discomfort, myalgia, neck pain, pain in extremity, and spinal pain.

g Post-marketing event

Adverse reactions reported in the pooled dataset for patients treated with nivolumab monotherapy (n = 2578). These reactions are presented by system organ class and by frequency.

Frequencies are defined as: very common ($\geq 1/10$); common ($\geq 1/100$ to $< 1/10$); uncommon ($\geq 1/1,000$ to $< 1/100$); rare ($\geq 1/10,000$ to $< 1/1,000$); very rare ($< 1/10,000$); not known (cannot be estimated from available post-marketing data). Within each frequency grouping, adverse reactions are presented in the order of decreasing seriousness.

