11.1.3 Toxicity

Toxicity and adverse events will be recorded using the NCI CTCAE v 4.0. All toxicities/AEs will be recorded from the initiation of protocol therapy through the follow-up period. The highest grade for any toxicity plus Grade 3 or 4 event for the same toxicity (if not the highest grade) will be reported during each cycle and during the safety follow-up period.

Eligible participants who did not receive any protocol treatment will be considered in-evaluable, replaced, and excluded from all analyses on toxicity.

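### Laboratory toxicity is to be summarised by CTCAE grade and raw nadir or maximum without the baseline grade, so abnormalities carried in after transplant can be mixed with those arising on treatment

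*Combined protocol and SAP*

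**What the plan says.** Safety and tolerability is a secondary objective (Section 1.2). Its general analysis plan is one sentence in Section 12.3.2. Toxicities are summarised by type, by "severity (by NCI CTCAE v4.0 and nadir or maximum values for lab measures", and then by "date of onset, duration, reversibility, and attribution". Section 11.1.3 adds the reporting rule for each cycle and for safety follow-up: "The highest grade for any toxicity plus Grade 3 or 4 event for the same toxicity (if not the highest grade) will be reported". Neither section mentions the grade at which a patient entered.

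On timing, the synopsis (Study Design) says: "Participants must initiate protocol therapy within 30 to 60 days post-ASCT". It adds a limited extension: "Study PI can grant exception for a patient to start as late as 75 days post-ASCT".

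Elsewhere the protocol does refer to baseline. Section 6.2 defines it as the last value before treatment. Section 5.9.2.1 and Table 6.2.1 give separate hepatic guidance for patients whose liver tests are already Grade 1 at entry, and Section 5.9.2.1 works from the rise in grade above baseline. Section 12.3.2 itself plans summaries of change before, during and after treatment, but only for the exploratory correlative measures.

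**The concern.** A worst value describes the effect of treatment only if the reader knows where the patient started. Here many patients may start away from normal, because dosing begins soon after high-dose therapy and the entry criteria allow for that. A patient who enters with a mildly low count, dips slightly after a dose and recovers can appear in the all-grade row at the grade already present at entry. The nadir will show the low value with nothing to indicate that it was low at the outset. With one arm, no control rate can be subtracted.

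What is at stake is how the all-grade laboratory rates and the nadir or maximum summaries are read. These will be among the main descriptions of tolerability for this combination after transplant.

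**Working it through.** The plan states no figure on this point, so there is none to reproduce. The check sets the entry criteria beside the protocol's own grade limits, then asks which planned summaries are exposed.

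**Step 1. What can be carried in**

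| Measure | Allowed at entry (Section 3) | Grade limits given in the protocol (Table 6.2.1, Section 5.9.2.1) | Consequence |
|---|---|---|---|
| ANC | 1000/mm³ or more | Grade 3: below 1000 to 500 | Lower grades can be carried in; Grade 3-4 cannot, on the qualifying test |
| Platelets | 50,000/mm³ or more | Grade 3: below 50,000 to 25,000 | Same |
| Hemoglobin | 8 g/dL or more | None given | Grade at entry cannot be placed from the documents |
| AST/ALT | Up to 2.5 x ULN | Grade 1: above ULN to 3.0 x ULN; Grade 3-4: above 5 x ULN | Grade 1 can be carried in; Grade 3-4 cannot |
| Peripheral neuropathy | Excluded from Grade 2 upward | Not a laboratory measure | Grade 1 can be carried in |

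**Step 2. Which summaries are exposed**

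- *Raw nadir and maximum.* Exposed. These are measured values and do not pass through the adverse event definition or attribution.
- *All-grade laboratory counts.* Exposed to the extent that a carried-in abnormality is recorded as an event after dosing.
- *Neuropathy.* The nadir wording does not apply to it. The exposure is through the highest-grade rule in Section 11.1.3, and only if a carried-in Grade 1 is recorded.
- *Grade 3-4 neutropenia and thrombocytopenia.* Largely protected. The entry floors lie just outside the Grade 3 ranges, so a later Grade 3-4 value is a worsening from the qualifying test. The remaining gap is a fall between that test and the first dose. The study calendar allows screening laboratory tests up to 14 days before therapy to serve as the Day 1 baseline.
- *Unacceptable-AE monitoring (Section 12.3.3).* Largely protected. It counts only events at least possibly attributed to therapy. Its specific hematologic triggers are Grade 4 neutropenia that does not resolve and Grade 3 or 4 thrombocytopenia with bleeding. Several non-hematologic items already refer to baseline.
- *18-month PFS.* Unaffected.

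**Step 3. Size**

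For one measure, let W be the number of patients whose grade rises by at least one level. Let C be the number who enter with an abnormal grade, do not rise above it, and are still recorded.

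- Reported all-grade count = W + C.
- Excess over the worsening rate = C/59.
- For each such patient: 1/59 = 0.017, or 1.7 percentage points.

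C can be as low as zero, if event recording screens all of these patients out. Its ceiling is the number who enter with an abnormal value and do not worsen. The documents do not give that number, so no total can be stated.

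**The case against.** The case against is substantial, and most of it stands.

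- **Attribution is also summarised.** The sentence in Section 12.3.2 goes on to attribution, which Section 7.7 records for each event. The Unrelated and Unlikely categories in Section 7.1 name the patient's clinical state and other treatments, which covers a recent transplant.
- **The adverse event definition filters.** Section 7.1 requires a new problem or an alteration in an existing one. Section 7.5 directs documentation to laboratory abnormalities that are clinically significant or serious, that interrupt or stop study drug, or that need corrective therapy. A stable, mild, pre-existing abnormality need not meet any of these.
- **No decision rests on the exposed summaries.** The monitoring rule and the primary test do not use them.

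A reader might therefore infer that transplant cytopenias will be reported as toxicity of the study drugs, or that Grade 3-4 hematologic rates will be inflated. The documents do not support either reading, given these filters and the entry floors. A reader might also object that all-grade rates would not match the nivolumab frequencies in Section 6.1.2, which count worsening from baseline. That is a list of expected toxicities, and no comparison with it is planned. The reference cited in Section 12.3.3 is the earlier post-transplant brentuximab vedotin trial and its Grade 3-4 rates.

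Three things remain. The Possible category in Section 7.1 expressly allows other causes, so a low count after a dose in a recently transplanted patient fits it readily. The adverse event definition sets no threshold of grade for a change, so a small dip within the same grade can qualify. Date of onset does not show the starting grade.

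**Conclusion.** The point holds as a limited reporting gap. The plan names a specific summary for laboratory toxicity that ignores the starting grade, in a population that may start with abnormal values. Raw nadirs, maxima and all-grade counts can therefore mix pre-existing with on-treatment abnormality. Existing safeguards reduce the mixing but do not remove it.

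The conclusion rests on three assumptions: some patients do enter with abnormal values inside the permitted limits; Sections 11.1.3 and 12.3.2 are the whole plan for summarising toxicity; and they are applied as written. The size is unknown beyond the per-patient step of 1.7 percentage points. No statement is made about Grade 3-4 anemia, because the documents give no hemoglobin grade limits. Sample size, power and the primary conclusion do not change.

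**What to change.** In Section 12.3.2, make the following the main laboratory toxicity summary, and present peripheral neuropathy the same way:

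- worst post-baseline CTCAE grade cross-tabulated by baseline grade, with baseline as defined in Section 6.2;
- the number and percentage of evaluable patients worsening by at least one grade;
- the number and percentage worsening to Grade 3-4.

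Keep the nadir or maximum and attribution as supplementary summaries.

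The cost is a few lines of analysis text and one set of tables. Laboratory values are already taken within 14 days before treatment, so no new sample or visit is needed. For neuropathy, the sponsor should confirm that the case report form separates Grade 0 from Grade 1 at entry, since the eligibility check needs only to show less than Grade 2. The change touches no dose, eligibility criterion or monitoring rule.
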